No formal statistical analysis will be performed to compare cohorts. This study is exploratory in nature; descriptive statistics will be tabulated by study phase and cohort and reviewed to evaluate all study endpoints.

4.1.2 *Summarization by Visit*

In general, data summarized by study visit will be based on the nominal, scheduled visit label as reported on the eCRF. Data collected for the last patient visit will be summarized separately and this summary will be labeled as “End of Treatment” in the analysis.

For laboratory data summaries, data summarized by study visit will be based on the nominal, scheduled visit label as reported on the eCRF when available. If the scheduled visit is not available, then all data collection, including unscheduled and early

termination visits, will be reassigned a study visit based on the actual days relative to baseline using the visit windows identified in [Table 3](#) below.

Table 3 Visit Windows for Analysis

Scheduled Visit	Target Study Day	Study Day Interval
Baseline	0	≤ 0
Cycle 1 Day 1	1	1
Cycle 1 Day 2*	2	2
Cycle 1 Day 8	8	3 – 11
Cycle 1 Day 15	15	12 – 18
Cycle 1 Day 22	22	19 – XX^{**}
Cycle 2 Day 1	$XX + 1$	$XX + 1$
Cycle 2 Day 8	$XX + 8$	$(XX + 2) – (XX + 11)$
<hr/>		
...		

*Note Cycle 1 is the only cycle with a schedule Day 2 visit

** Day 22 is the last scheduled visit within each cycle, and the end of the study interval (XX) is calculated as the day before the start of the subsequent cycle.

If more than one value is mapped to the same visit, the value collected closest to the target study day will be considered for summarization. If two values collected on different days are mapped to the same scheduled visit and are equidistant from the target study day, the earlier of the values will be considered. The visit displayed on subject data listings will be reflective of the scheduled visit label as reported on the eCRF. Study days relative to baseline will be displayed for each visit to indicate to which visit the assessment may have been reassigned, if any.

Otherwise, data collected at unscheduled visits will not be included in by-visit summaries but will be considered when endpoint derivations potentially include multiple visits (e.g., determination of baseline value, determination of worst post-baseline value, etc.). All data will be included in patient listings.

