4.7.3 Plasma Pharmacokinetic Parameters

Plasma concentration-time data will be analyzed by non-compartmental analysis using Base SAS® software, version 9.4 or higher. The following PK parameters will be calculated for nanatinostat and ganciclovir, where data permit:

Table 5 Pharmacokinetic Parameters

C_{\max}	Maximum observed concentration.
T_{\max}	Time of maximum observed concentration.
T_{last}	Time of last measurable concentration
AUC_{0-t}	Area under the concentration-time curve from time 0 to the last measurable observed concentration (C_t), calculated using the linear trapezoidal rule.
$AUC_{0-\infty}$	Area under the concentration-time curve from time 0 extrapolated to infinity, calculated as $[AUC_{0-t} + (C_{\text{last}} / \lambda_z)]$ where C_{last} is the last observed measurable concentration (for Cycle 1 Day 1 only) (if applicable)
AUC_{0-6h}	Area under the concentration-time curve from time 0 to 6 hours (if applicable for nanatinostat)
AUC_{0-7h}	Area under the concentration-time curve from time 0 to 7 hours (if applicable for ganciclovir)
AUC_{0-8h}	Area under the concentration-time curve from time 0 to 8 hours (if applicable for nanatinostat and ganciclovir)
AUC_{0-24h}	Area under the concentration-time curve from time 0 to 24 hours (if applicable)
λ_z	Apparent terminal elimination rate constant, where λ_z is the magnitude of the slope of the linear regression of the log concentration versus time profile during the terminal phase.
$t_{1/2}$	Apparent terminal elimination half-life, calculated as: $\ln(2) / \lambda_z$.
CL/F	Apparent total body clearance, calculated as: Dose / $AUC_{0-\infty}$ for C1D1, and Dose / AUC_{0-24h} for Cycle 2 Day 1.
V_z/F	Apparent volume of distribution during the terminal phase, calculated as: Dose / $[\lambda_z * AUC_{0-\infty}]$ for C1D1, and Dose / $[\lambda_z * AUC_{0-24h}]$ for Cycle 2 Day 1.
$\%AUC_{\text{ext}}$	Percentage of $AUC_{0-\infty}$ due to extrapolation; $AUC_{0-\infty}$, CL/F and V_z/F values on C1D1 will be flagged and excluded from summary statistics where $\%AUC_{\text{ext}} > 20\%$.
$AR_{C_{\max}}$	Accumulation ratio based on C_{\max} between Cycle 2 Day 1 and Cycle 1 Day 1
$AR_{AUC_{0-24h}}$	Accumulation ratio based on AUC_{0-24h} between Cycle 2 Day 1 and Cycle 1 Day 1

Actual sampling times will be used for the estimation of all plasma PK parameters, and all concentrations will be included in the analysis (including concentrations collected outside predefined collection windows).

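### Cycle 2 Day 1 CL/F, Vz/F and the AUC accumulation ratio are defined from AUC0-24h, but sampling that day stops at 8 hours and no rule covers 8 to 24 hours

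*SAP*

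**What the plan says.** SAP 4.7.3, Table 5, lists "Area under the concentration-time curve from time 0 to 24 hours (if applicable" and uses it three times for Cycle 2 Day 1:

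- CL/F: "Apparent total body clearance, calculated as" dose over AUC0-infinity "for C1D1, and Dose / AUC_{0-24h} for Cycle 2 Day 1".
- Vz/F: "Apparent volume of distribution during the terminal phase, calculated as: Dose" over lambda_z times the area, again with AUC0-infinity on Cycle 1 Day 1 and AUC0-24h on Cycle 2 Day 1.
- AUC accumulation ratio: "Accumulation ratio based on AUC_{0-24h} between Cycle 2 Day 1 and Cycle 1 Day 1".

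The AUC0-infinity row carries the limit "for Cycle 1 Day 1 only) (if applicable". The exclusion of values with more than 20% extrapolation is likewise written for Cycle 1 Day 1. The whole table is introduced by "The following PK parameters will be calculated for nanatinostat and ganciclovir, where data permit".

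Protocol 6.4.1, Table 14, gives plasma samples on Day 1 of Cycles 1 and 2 at pre-dose, 0.5, 1, 2, 4, 6 and 8 hours. A next-day pre-dose sample is listed for Cycle 1 only. The Schedule of Events (Protocol 7, Table 15) has only Days 1 and 15 in Cycle 2. The footnote to SAP Table 3 (SAP 4.1.2) agrees: "Note Cycle 1 is the only cycle with a schedule Day 2 visit".

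**The concern.** A parameter defined over 24 hours is paired with a profile that stops at 8. On Cycle 1 Day 1 the next-day pre-dose sample supplies a point near 24 hours. On Cycle 2 Day 1 nothing does, and neither SAP 4.7.1 (data handling) nor 4.7.3 says how to get from 8 to 24 hours. Two analysts following the SAP could therefore report different results, or none.

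The two halves of the accumulation ratio may also be computed by unlike methods, which can push the ratio below 1 with no change in kinetics. PK of both drugs is a secondary objective. SAP 4.7.2 names serial Cycle 2 Day 1 profiles for some Phase 2 capsule patients and all tablet-cohort patients, and the tablet cohort exists to assess exposure. A spurious fall in exposure, or a clearance that is too high, would be a misleading result there.

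**Working it through.** The documents give no numerical target, so the check has two parts: coverage, then the effect of each way of filling the gap.

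**Coverage.** Cycle 2 Day 1 is sampled over 0-8 h, so 24 - 8 = 16 of 24 hours are unsampled. The next Cycle 2 sample is on Day 15.

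**Model for ganciclovir.** One compartment, oral, once daily (Protocol 3.2.4). The documents give no half-life; 3, 4 and 5 h with an absorption rate ka of 1/h are assumptions. With k = ln 2 / half-life and A = ka/(ka - k):

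- Cycle 1 Day 1: C(t) = A(e^(-kt) - e^(-ka t)).
- Cycle 2 Day 1 (steady state): the same, with each exponential divided by 1 - e^(-24 x rate).

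Both are sampled at the Table 14 times and integrated by the linear trapezoidal rule. The Cycle 1 area to 24 h adds one trapezoid, 16 x (C8 + C24)/2. Extrapolation on Cycle 2 Day 1 adds C8(1 - e^(-16 lambda_z))/lambda_z, with lambda_z fitted to the 4, 6 and 8 h points. Areas are in arbitrary units.

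| Quantity | 3 h | 4 h | 5 h |
|---|---|---|---|
| True AUC0-24h, Cycle 1 | 4.306 | 5.662 | 6.913 |
| True AUC0-24h, Cycle 2 | 4.328 | 5.771 | 7.214 |
| True ratio | 1.005 | 1.019 | 1.043 |
| Cycle 1 trapezoid, 0-8 h | 3.398 | 3.971 | 4.390 |
| Cycle 1 linear area to 24 h | 5.074 | 6.538 | 7.784 |
| Same, relative to truth | 1.18 | 1.15 | 1.13 |
| Cycle 2 trapezoid, 0-8 h | 3.417 | 4.055 | 4.600 |
| Cycle 2 extrapolated to 24 h | 4.322 | 5.786 | 7.256 |
| Same, relative to truth | 0.999 | 1.003 | 1.006 |

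For the 3 h column, the Cycle 1 linear area is 3.398 + 8 x (0.2044 + 0.0051) = 5.074.

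**What each choice returns.**

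| Choice | 3 h | 4 h | 5 h |
|---|---|---|---|
| Ratio: Cycle 2 extrapolated / Cycle 1 linear | 0.852 | 0.885 | 0.932 |
| Ratio: extrapolated on both days | 1.005 | 1.019 | 1.043 |
| Ratio: Cycle 2 stopped at 8 h / Cycle 1 linear | 0.673 | 0.620 | 0.591 |
| Ratio: AUC0-8h on both days | 1.006 | 1.021 | 1.048 |
| CL/F error if the 8 h area is used as AUC0-24h | +27% | +42% | +57% |
| Extrapolated share of Cycle 2 AUC0-24h | 21% | 30% | 37% |

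For example, at 4 h: 5.786/6.538 = 0.885, and 5.771/4.055 - 1 = 0.42.

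**Nanatinostat.** Protocol 1.8 gives a median half-life of 1.8 h (range 1.1-7.8 h) and a median Tmax of 1 h. In the same kind of model the share of AUC0-24h after 8 h is 6% at 1.8 h, 1% at 1.1 h and 43% at 7.8 h. On the 4-on/3-off schedule the last Cycle 1 dose is on Day 25, so Cycle 2 Day 1 (Day 29) comes 4 x 24 = 96 h later: 53 half-lives at 1.8 h and 12 at 7.8 h. Both profiles start from near zero, so their ratio says little about accumulation.

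**The case against.** The strongest reply is that what cannot be observed can still be estimated. The SAP already computes lambda_z, and in the model extrapolation to 24 h is within 1% of truth. Applied on both days it recovers the true ratio. That stands: the defect is a missing rule and a mismatch of methods, not an impossible parameter. In this model the Cycle 1 area, despite its 24-hour sample, is the less accurate of the two.

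Second, the plan hedges. AUC0-24h is marked as conditional, all parameters are subject to what the data allow, and AUC0-8h and a Cmax accumulation ratio are already listed. Empty cells would be consistent with the text. That also stands, but it leaves the choice open in a document meant to avoid post hoc decisions.

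Third, a reader might infer that the report will show CL/F 27-57% too high, or a ratio near 0.6. The documents do not support that. It requires the 8-hour area to be reported as AUC0-24h, and Table 5 lists AUC0-t, AUC0-8h and AUC0-24h separately.

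Fourth, a reader might infer that this holds for every patient under every protocol version. SAP 4.7.2 refers to Table 14 in all versions and only one is available, although the Day 2 footnote to SAP Table 3 is not tied to a version.

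Fifth, the Cycle 1 24-hour point may not exist for nanatinostat. At a mean Cmax of 54 ng/mL for 20 mg (Protocol Table 4), the modelled 24-hour level is about 0.01 ng/mL. The quantification limit is not given; if the sample is below it and treated as post-dose, SAP 4.7.1 sets it to missing.

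Finally, the results are descriptive, and the dose-proportionality model in SAP 4.7.4 uses Cmax, AUC0-infinity and AUC0-6h, none of the three outputs at issue.

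**Conclusion.** The point holds as an unstated rule. In the protocol version supplied, Cycle 2 Day 1 CL/F, Vz/F and the AUC accumulation ratio are defined from an interval of which two thirds is unsampled, and the SAP does not say how to fill it. Taken strictly the outputs are empty; taken loosely they depend on the programmer.

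The realistic bias is in the ganciclovir ratio: about 0.85-0.93 against a true 1.01-1.04 when an extrapolated Cycle 2 area is divided by the linear Cycle 1 area, which is itself 13-18% too high. This rests on a one-compartment model, an assumed half-life of 3-5 h, ka of 1/h and once-daily steady state. Nanatinostat is little affected at its median half-life, but its ratio should not be called accumulation. Severity is minor to moderate: secondary, descriptive outputs, cheaply repaired.

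**What to change.** In SAP Table 5:

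1. Replace the AUC0-24h accumulation ratio with one based on AUC0-8h on both days. For nanatinostat, label it a Cycle 2/Cycle 1 exposure ratio, because Cycle 2 Day 1 follows the 3-day dosing holiday.
2. State one rule per drug for Cycle 2 Day 1 CL/F and Vz/F. For ganciclovir, use AUC0-24h by lambda_z extrapolation from 8 h. For nanatinostat, use AUC0-infinity, and lift the Cycle 1 Day 1 restriction on that row accordingly.
3. Flag these values, and exclude them from summaries, when the extrapolated share exceeds 20%.

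The cost is SAP wording and programming, with no extra samples. The drawback is lost ganciclovir CL/F and Vz/F values: the modelled share is 21%, 30% and 37% at 3, 4 and 5 h, so if the half-life lies in that range many profiles could drop out of those summaries. The AUC0-8h ratio would be unaffected.

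An alternative for ganciclovir is to use the Cycle 2 Day 1 pre-dose level as the 24-hour value, with log-linear interpolation from 8 h; the model puts this at 0.990-0.991 of truth. It is open only if the rule in Protocol 12.4.1 that sets quantifiable pre-dose concentrations to zero is limited to Cycle 1 Day 1. It also needs the previous dose to have been taken about 24 h earlier, so profiles after a hold would be left out.

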3.5. Dose Adjustments/Modifications/Delays

Details on dose adjustments, modifications, and delays are outlined in [Section 5.1.8](#) and [Section 5.2.5](#).

Patients who have had a dose hold should continue to follow all assessments called for in the Schedule of Events (i.e., if a patient undergoes a dose interruption, this will not delay conduct of any study procedures).

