5.1.8. Dose Adjustments/Modifications/Delays

Given the expectation that both study drugs are required for activity, both agents will be held and restarted in parallel unless toxicity is clearly associated with VRx-3996 and there is clinical justification to continue dosing with valganciclovir alone. For non-hematologic toxicity requiring dose modification see [Table 12](#).

Table 12: Requirements for Dose Hold Secondary to Non-Hematologic Toxicity

Toxicity (CTCAE)	Requirement for Dose Hold
Grade 1 or 2	No dose hold required
Grade 3+	Hold subsequent dosing until toxicity has resolved to at least Grade 1 or baseline

In the event that any of the following hematologic AEs are observed on study, the dose of VRx-3996 and valganciclovir will be held:

- ANC <500 cells/ μ L
- PLT count <35,000/ μ L
- Hemoglobin (HGB) is <8 g/dL

If a hold is implemented for study drug-related toxicity, patients may restart study drugs only if the following conditions are met or if agreed with the Medical Monitor:

- The AE has resolved to at least Grade 1 or baseline for non-hematologic AEs and Grade ≤ 2 hematologic toxicity related to study drug
- The AE is not expected to recur in the opinion of the Investigator with subsequent study drug administration based on an intervention such as prophylactic use of appropriate treatment (e.g., prophylactic anti-emetics), or a reduction in the dose of one or both of the study drugs
- Continued administration of study drugs is considered to be in the patient's best interest based on the opinion of the study Investigator

Patients should be followed up approximately twice weekly for resolution of the toxicity. Study days will continue to accrue during dose holds and other scheduled procedures as per [Table 15](#) should not be delayed. If the dose is held for more than 14 days, the Investigator should consult with the Medical Monitor before dosing resumes.

If a patient has multiple dose interruptions for study drug toxicity or has had to interrupt for more than 14 days, a dose reduction should be considered. Dose reduction for VRx-3996 will be in 10 mg increments and for valganciclovir from 900 mg to 450 mg. Re-escalation of study drug dose may only be performed after approval by Medical Monitor.

There are additional criteria for modification of the valganciclovir dose based on renal function as outlined in [Section 5.2.3](#).

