5.4. Vomited Doses

If a scheduled dose of VRx-3996 or valganciclovir is vomited, the patient should contact the site for consideration of anti-nausea medication and dosing should resume with the next scheduled dose. No replacement dose should be given.

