7. SCHEDULE OF EVENTS

The study procedures for the Phase 1b and Phase 2 portions of the study will follow those outlined in [Table 15](#).

Table 15: Schedule of Events

Cycle	SR	1					2		3+		ET	ST	SV
Cycle Day		1	2	8	15	22	1	15	1	15			
Assessment													
Informed consent	X												
Medical history (includes donor data)	X												
EBER/histology sample	X						[X]		[X]		[X]		
Height	X												
Physical examination	X												
Symptom-directed exam		X	X	X	X	X	X	X	X	X	X	X	
Vital signs	X	X	X	X	X	X	X	X	X	X	X	X	
Performance status	X	X	X	X	X	X	X	X	X	X	X	X	
Adverse events		X	X	X	X	X	X	X	X	X	X	X	
Concomitant medications	X	X	X	X	X	X	X	X	X	X	X	X	
Urinalysis	X	X		X	X	X	X	X	X	X	X	X	
Hematology	X	X	X	X	X	X	X	X	X	X	X	X	
Chemistry	X	X	X	X	X	X	X	X	X	X	X	X	
Coagulation	X	X		X	X	X	X	X	X	X	X	X	
Serum pregnancy test	X												
Urine pregnancy test		X					X		X				
12-lead ECG	X	X	X	X	X	X	X	X	X	X	X	X	
Head CT/MRI	X												
Disease assessment	X								X		X		
PK sample(s)		X	X		X		X	X					
Urine PK sample collection		X											
Hepatitis B antigen/antibodies	X												
Hepatitis B DNA PCR	X												
Hepatitis C antibodies	X												
Hepatitis C qPCR	X												

Cycle	SR	1				2		3+		ET	ST	SV
HLA testing		X										
Exploratory Biomarkers												
-Histone H3 acetylation		X	X	X			X					
-Immune profile		X			X		X		X		X	
-EBV and CMV qPCR		X	X	X	X	X	X		X			
VRx-3996/valganciclovir distribution		X					X		X			
VRx-3996/valganciclovir return							X				X	
VRx-3996/valganciclovir compliance assessment		X	X	X	X	X	X	X	X	X		
Survival and follow-up assessment and disease status												X

Study assessments may be performed ± 3 days of the recommended date (however the DLT assessment period should include a full 28 days). Study visits with PK assessments should occur on days that the patient will take both study drugs, VRx-3996 and valganciclovir. End of Treatment (ET) Visit assessments (if needed) will be the same as for the Safety Follow-Up Visit. Safety Follow-Up Visit will be performed 28 ± 7 days after last dose.

SR – Screening (within 21 days of Cycle 1 Day 1)

ET – End of Treatment

ST – Safety follow-up

SV – Survival follow-up contact (performed at least every 3 months after safety follow-up assessment)

X – Required

[X] – Biopsy tissue samples taken per standard of care during study participation and samples taken at the time of relapse should be submitted to the central pathology lab for review.

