4.7.1 Data Handling

Plasma concentrations that are below the limit of quantification (BLQ) will be treated as zero for the calculation of descriptive statistics. If the calculated mean concentration is BLQ, the mean value will be reported as BLQ, and the SD and CV% will be reported as not applicable. For PK analysis, all predose BLQ values will be treated as zero and all postdose BLQ values will be treated as missing. If consecutive BLQ concentrations are followed by quantifiable concentrations in the terminal phase, those quantified concentrations after BLQ concentrations will be treated as missing. Missing concentrations will be treated as missing from the PK parameter calculations.

For Cycle 1 Day 1 only, if the pre-dose value is $> 5\%$ of C_{max} , the subject will be flagged in all associated data listings and the affected profile will be excluded from all PK summaries and statistical evaluations.

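### The SAP has no rule for PK profiles whose dose was vomited, missed or held on the sampling day, so such profiles enter the exposure summaries

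*SAP*

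**What the plan says.** SAP 4.2 places a patient in the PK Analysis Set on the strength of one analysed post-dose sample. SAP 4.7.3 uses actual sampling times for all parameters and adds that "all concentrations will be included in the analysis (including concentrations collected outside predefined collection windows".

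The SAP does restrict PK data in other ways:
- Section 4.7.1 drops a Cycle 1 Day 1 profile whose pre-dose value exceeds 5% of Cmax.
- For the non-compartmental analysis (NCA), 4.7.1 sets post-dose BLQ values to missing, along with quantifiable values that follow consecutive BLQ values in the terminal phase.
- Section 4.7.2 leaves badly mistimed samples out of the concentration summaries.
- Section 4.7.3 leaves Cycle 1 Day 1 AUC0-inf, CL/F and Vz/F out of summaries when extrapolation exceeds 20%.

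For the concentration summaries, as opposed to the NCA, BLQ values "will be treated as zero for the calculation of descriptive statistics". Section 4.7.2 also lets nominal time stand in for a missing dosing time.

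On vomited doses, Protocol 5.4 says "No replacement dose should be given" and does not mention PK. On holds, Protocol 3.5 says that "if a patient undergoes a dose interruption, this will not delay conduct of any study procedures", and 5.1.8 repeats the principle. The notes to Protocol Tables 14 and 15 say instead that "Study visits with PK assessments should occur on days that the patient will take both study drugs, VRx-3996 and valganciclovir". The general visit window is stated as: "Study assessments may be performed ± 3 days of the recommended date".

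**The concern.** None of these exclusions asks whether the dose behind the samples was swallowed and retained. Protocol 1.8 lists nausea among the most prevalent adverse events of the earlier single-agent study. Protocol 3.12 does not initially allow prophylaxis against study-drug toxicity, apart from tumour lysis prophylaxis. Vomiting on a PK day is therefore foreseeable. If it happens early, serial samples are still drawn and the profile enters Cmax, AUC, CL/F, the accumulation ratios (4.7.3) and the dose-proportionality model (4.7.4).

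For a hold longer than the visit window, the protocol gives a site two answers on whether to draw PK samples. A site that follows 3.5 produces undosed samples, and the concentration tables average these as zeros.

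PK is a secondary objective. Protocol 3.3 sets up the tablet cohort of about 10 to assess exposure and its comparability with capsules. In groups of that size, and in Phase 1b cohorts of at most 7, one or two failed doses carry weight. Without a rule, any later exclusion would be decided after seeing the data, which SAP section 1 says the plan exists to avoid.

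**Working it through.** The plan states no figure to reproduce. The check is a model illustration plus a reading of the BLQ rules.

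**Inputs from Protocol 1.8.** Median half-life is 1.8 h and median Tmax is 1 h. Table 4 gives, at 20 mg, a median Tmax of 4 h (n = 3) and a mean Cmax of 54 ng/mL. AUC CV is 57% at 10 mg and 74% at 40 mg. The tablet cohort has n of about 10 (Protocol 3.3).

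**Assumptions.** One-compartment oral model; vomiting at time t removes all drug not yet absorbed; 1 to 3 of 10 patients affected.

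**One vomited dose.** ke = ln 2/1.8 = 0.385 per h. Tmax 1 h requires ln(ka/ke)/(ka − ke) = 1, so ka = 2.06 per h. The absorbed fraction is f = 1 − exp(−ka·t). AUC is multiplied by f and CL/F by 1/f.

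| Emesis at | f | AUC change | CL/F factor |
|---|---|---|---|
| 0.25 h | 0.403 | −60% | 2.48 |
| 0.5 h | 0.644 | −36% | 1.55 |
| 1 h | 0.873 | −13% | 1.15 |
| 2 h | 0.984 | −2% | 1.02 |

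The 20% extrapolation rule would not catch these profiles. With this half-life, about exp(−0.385 × 8) = 0.05 of the area lies beyond 8 h, whether or not part of the dose was lost.

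**Group effect.** With k of 10 affected, the geometric mean AUC is multiplied by f^(k/10).
- Emesis at 0.25 h: 0.403^0.1 = 0.913 (−9%) for one patient; 0.403^0.3 = 0.761 (−24%) for three.
- Emesis at 2 h: −0.2% to −0.5%.
- With Tmax 4 h (ka = 0.151 per h), emesis at 2 h leaves f = 0.261, and one patient of 10 gives 0.261^0.1 = 0.874 (−12.6%).

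**Against sampling error.** The SE of the log geometric mean is √ln(1 + CV²)/√10. This is 0.530/3.162 = 0.17 for CV 57% and 0.661/3.162 = 0.21 for CV 74%. A 9% fall is −0.091 on the log scale, about 0.4 to 0.5 SE. A 24% fall is −0.273, about 1.3 to 1.6 SE.

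**A held nanatinostat dose.** Cycle 1 Day 1 is the first dose and cannot fall in a hold. Cycle 1 Days 2 and 15 and Cycle 2 Day 15 have only pre-dose and 2 h samples. The serial profile at stake is Cycle 2 Day 1. On the 4-days-on, 3-days-off schedule it falls at least 96 h after the last dose, and the modelled residue is nil. Even at the longest half-life cited (7.8 h), it is 54 × exp(−(ln 2/7.8) × 95) = 0.01 ng/mL. If every post-dose value is BLQ, the NCA treats all of them as missing and computes no AUC or CL/F. The by-time means count them as zero: with 1, 2 or 3 of 10 on hold, each post-dose mean falls by 10%, 20% or 30%.

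The documents give neither the LLOQ nor the ganciclovir half-life, so the same case for ganciclovir cannot be sized.

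**The case against.** The SAP never says that it keeps profiles after a failed dose. The all-concentrations sentence is about collection windows, and other exclusions exist. On holds, the PK-specific instruction appears in the notes to Tables 14 and 15 and could be read as overriding the general rule, with the visit window covering short holds. Nausea appeared dose related over 5 to 160 mg, and the tablet cohort receives 20 mg. The Safety Review Committee may also introduce anti-emetic prophylaxis (Protocol 3.12). The SAP reports medians and ranges as well as means, compares no cohorts formally (4.1) and claims no equivalence (4.6.5.7).

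Much of this stands. Inclusion follows from a general sentence plus silence, and likelihood cannot be judged without a rate. The hold conflict is confined to holds that outlast the window, although 5.1.8 does foresee holds beyond 14 days. It does not close the gap: applied as written, the rules admit such profiles, and the dose-proportionality model fits individual patient data without regard to whether the dose was retained.

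A reader might infer that held doses also inflate CL/F. For nanatinostat they do not, because post-dose BLQ is missing in the NCA. A reader might also infer that one or two failed doses would look like a formulation effect. At these CVs, one patient vomiting at 0.25 h (Tmax 1 h) moves the geometric mean by only about half a standard error.

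**Conclusion.** The gap is real and moderate. The SAP has no dosing-integrity criterion for PK profiles, so exposure summaries may be biased; the documents do not show that they are. With Tmax 1 h, the AUC loss in an affected patient runs from about 60% (emesis at 0.25 h) to 2% (2 h). The geometric mean of 10 falls by about 9% to 24% if one to three patients vomit at 0.25 h, and hardly at all if they vomit at 2 h. Slower absorption, as the three patients at 20 mg suggest, makes the effect larger. These figures rest on the one-compartment model and on assumed counts. For held nanatinostat doses, the effect is limited to by-time mean concentrations. Separately, Protocol 3.5 and 5.1.8 conflict with the PK-day notes for holds longer than the ±3-day window.

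**What to change.** In SAP 4.7.1 and 4.7.3, keep every profile in the listings. Flag, analyte by analyte, any profile in which (a) that analyte's oral dose was not taken in full on the PK day, or (b) emesis occurred within a stated time of dosing. Exclude flagged profiles from the concentration summaries, parameter summaries, accumulation ratios and dose-proportionality model. Report how many were excluded and why, and repeat the summaries with all profiles as a sensitivity analysis.

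Fix the emesis cut-off before the PK data are reviewed. Twice the analyte's median Tmax is one option, but the SAP must say which Tmax: 1 h gives 2 h, while the 4 h median at 20 mg gives 8 h, the whole Day 1 sampling period.

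The SAP already describes parts of the conduct in the past tense, so the rule should use the emesis and dosing times already recorded. It should also state how emesis on the PK day with no clock time is handled.

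In the protocol, reconcile 3.5 and 5.1.8 with the notes to Tables 14 and 15 for holds that outlast the visit window.

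The cost is a short SAP paragraph, one extra set of summaries and one protocol clarification. The downside is that a few profiles leave the main summaries, and more would leave under a long cut-off.
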